APPENDIX: Clinical Data Repository

1. Will you be obtaining data from the UVa Clinical Data Repository (CDR)? yes

CATEGORY	DATA ELEMENTS	CHECK ALL THAT APPLY
Demographics	e.g. Gender, race, age	
Administrative	e.g. Includes payor, payscale, length of stay, fact of visits (inpatient or outpatient), locations of service (inpatient or outpatient), providers	
Financial	e.g. Charges or costs associated with care	x
Clinical Data	e.g. Diagnoses	
	e.g. Procedures	
	e.g. Mortality	
	e.g. Laboratory / Microbiology Results	
	e.g. Medications	
	e.g. Vitals, Height / Weight, Other Clinical Parameters	
	e.g. Other (specify)	
Narrative Reports	e.g. Includes discharge summaries, pathology reports, operative notes, etc.	
Other	Explain:	

Data and Safety Monitoring Plan

INSTRUCTIONS:

If you have any questions completing this section call [name] for assistance.

A Sponsor is defined as entity that will receive data prior to publication.

1. Definition:

1.1 How will you define adverse events (AE) for this study?

An adverse event will be considered any undesirable sign, symptom or medical or psychological condition **only if the event is considered to be related** to the investigational drug/device/intervention. Medical condition/diseases present before starting the investigational drug/intervention will be considered adverse events only if they worsen after starting study treatment/intervention. An adverse event is also any undesirable and unintended effect of research occurring in human subjects as a result of the collection of identifiable private information under the research. Adverse events also include any problems associated with the use of an investigational device that adversely affects the rights, safety or welfare of subject s.

1.2 How will you define serious adverse events?

A serious adverse event will be considered any undesirable sign, symptom, or medical condition which is fatal, is life-threatening, requires or prolongs inpatient hospitalization, results in persistent or significant disability/incapacity, constitutes a congenital anomaly or birth defect, is medically significant and which the investigator regards as serious based on appropriate medical judgment. An important medical event is any AE that may not result in death, be life-threatening, or require hospitalization but may be considered an SAE when, based upon appropriate medical judgment, it may jeopardize the patient and may require medical or surgical intervention to prevent one of the outcomes listed in the definitions of SAEs.

1.3 What is the definition of an unanticipated problem?

Do not change this answer

An unanticipated problem is any event, experience that meets ALL 3 criteria below:

- Is unexpected in terms of nature, severity or frequency given the research procedures that are described in the protocol-related documents AND in the characteristics of the subject population being studies
- Related or possibly related to participation in research. This means that there is a reasonable possibility that the incident may have been caused by the procedures involved in the research study.
- The incident suggests that the research placed the subject or others at greater risk of harm than was previously known or recognized OR results in actual harm to the subject or others

○ What are the definitions of a protocol violation and/or noncompliance?

Do not change this answer

A **protocol violation** is defined as any change, deviation, or departure from the study design or procedures of research project that is NOT approved by the IRB-HSR prior to its initiation or implementation. Protocol violations may be major or minor violations.

Noncompliance can be a protocol violation OR deviation from standard operating procedures, Good Clinical Practices (GCPs), federal, state or local regulations. Noncompliance may be serious or continuing.

Additional Information: see the IRB-HSR website at http://www.virginia.edu/vpr/irb/HSR_docs/Forms/Protocol_Violations_%20Enrollment_Exceptions_Instructions.doc

- **If pregnancy occurs how will this information be managed?**

Unanticipated Problems- will follow Unanticipated Problem recording and reporting procedures outlined in section 3.

- **What is the definition of a Protocol Enrollment Exception?**

____ Protocol has a sponsor or a Data & Safety Monitoring Board (DSMB) outside of UVa. An enrollment exception is the DSMB or sponsor’s prospective approval for the enrollment of a research subject that fails to meet current IRB-HSR approved protocol inclusion criteria, or falls under protocol exclusion criteria. Enrollment exceptions only apply to a single individual. Such a request should be rare and justified in terms of serving the best interests of the potential study participant.

- **What is the definition of a data breach?**

Do not change this answer

A data breach is defined in the HITECH Act (43 USC 17932) as an unauthorized acquisition, access, or use of protected health information (PHI) that compromises the security or privacy of such information.

Additional Information may be found on the IRB-HSR Website: [Data Breach](#)

2. Identified risks and plans to minimize risk

2.1 What risks are expected due to the intervention in this protocol?

Expected Risks related to study participation.	Frequency

 • Constipation 	Occurs frequently

 • Flatulence (gas) 	Occurs frequently

• Dyspepsia (upset stomach)	Occurs frequently
• Anemia (low blood count	Occurs infrequently
• Urinary retention	Occurs infrequently
• Back pain	Occurs infrequently
Hypokalemia (low potassium	Occurs infrequently
Reproductive Risks Specify potential reproductive risks here	Minimized due to the requirements of this protocol.
Violation of subject’s privacy and confidentiality	Minimized due to the requirements of the privacy plan in this protocol

The drug has shown an increase in heart attack when used long term, but no evidence of this has been seen with short-term use.

2.2 List by bullet format a summary of safety tests/procedures/observations to be performed that will minimize risks to participants:

- adequate screening
- AE monitoring at each visit

2.3 Under what criteria would an INDIVIDUAL SUBJECT’S study treatment or study participation be stopped or modified

At subject, PI or sponsor’s request

Treatment would be stopped if the subject had a serious adverse event deemed related to study,

○ **Under what criteria would THE ENTIRE STUDY need to be stopped.**

Per IRB, PI,

2.5 What are the criteria for breaking the blind/mask?

Other: the purpose of the final analysis, the official clinical database will not be unblinded until medical/scientific review has been completed at the end of the entire study, protocol violators have been identified (if appropriate), and data has been declared complete.

How will subject withdrawals/dropouts be reported to the IRB prior to study completion?

IRB-HSR continuation status form

3. Adverse Event / Unanticipated Problem Recording and Reporting

3.1 Will all adverse events, as defined in section 1.1, be collected/recorded? No

▶ **IF NO, what criteria will be used?**

Only adverse events that are deemed related AND serious

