- Subjects will be randomized to either the alvimopan or placebo group
- Alvimopan or placebo administered orally pre-operatively
- Alvimopan or placebo administered orally or per NG twice daily post-operatively for up to seven days post-operatively, or until the time of discharge, whichever occurs first, to a maximum of 15 doses
- All intraoperative data recorded on the anesthesia record will be collected prospectively.
- BIS scores, when available, will be collected at the completion of surgery.
- Neuromonitoring data (ex. latency, amplitude, significant signal changes) will be collected at the completion of surgery.
- Postoperatively, visual analog scale (VAS) scores will be assessed daily at morning rounds.
- Additionally, nutritional intake and in hospital complications will be recorded, as will the patient's report of pain (on the 0-10 pain scale), time to first solid intake, time to first flatus and bowel movement (**primary outcome**), time to first ambulation, and consumption of all pain medications (intravenous and by mouth).
- ICU stay and hospital stay will be noted Initial post-op pain management orders will be entered by the Anesthesiologist
- to standardize opioid requirements, patients will initially be ordered hydromorphone as the intravenous opioid of choice (PCA and prn), and will only be changed (fentanyl) if specifically requested by the primary service.
- Patients will also be ordered oxycodone as the initial PO opioid of choice, and only changed to other medications (hydrocodone) if specifically requested by the primary service
- At the completion of hospitalization, QR40 will be used to assess the patients' pain and quality of life at discharge.

Total patient charges will be extracted from the University of Virginia's Clinical Data Repository.

2. Will you be using data/specimens in this study that were collected previously, with the use of a research consent form, from another research study? No

3. Will any of the procedures listed in item # 1 have the potential to identify an incidental finding? This includes ALL procedures, assessments and evaluations that are being done for RESEARCH PURPOSES that may or may not be considered investigational. No

4. Do any of the procedures listed above, under question # 1, utilize any imaging procedures for RESEARCH PURPOSES? No

5. Will you be using viable embryos? No

6. Will you be using embryonic stem cells? No

9. Are any aspects of the study kept secret from the participants? Yes

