3.6 When will the recording/reporting of adverse events/unanticipated problems end?

End of study drug/device/intervention/participation

3.7 How will Adverse Events, Unanticipated Problems, Protocol Violations and Data Breaches be reported? Complete the table below to answer this question

Type of Event	To whom will it be reported:	Time Frame for Reporting	How reported?

Any internal event resulting in death that is deemed DEFINITELY related to (caused by) study participation An internal event is one that occurs in a subject enrolled in a UVa protocol
	IRB-HSR	Within 24 hours	IRB Online and phone call www.irb.virginia.edu/

Internal, Serious, related, Unexpected adverse event
	
IRB-HSR
	
Within 7 calendar days from the time the study team received knowledge of the event.
 
Timeline includes submission of signed hardcopy of AE form.
	
IRB Online
 
www.irb.virginia.edu/

Unanticipated Problems that are not adverse events or protocol violations This would include a Data Breach.
	
IRB-HSR
	
Within 7 calendar days from the time the study team received knowledge of the event.
	
Unanticipated Problem report form.
 
http://www.virginia.edu/vprqs/irb/HSR_docs/Forms/Reporting_Requirements-Unanticipated_Problems.doc)

Protocol Violations/Noncompliance The IRB-HSR only requires that MAJOR violation be reported, unless otherwise required by your sponsor, if applicable.
 
OR
 
Enrollment Exceptions See definition- only allowed if there is a commercial sponsor or a DSMB that has granted the enrollment exception.
	
IRB-HSR
	
Within 7 calendar days from the time the study team received knowledge of the event.
	
Protocol Violation, Noncompliance and Enrollment Exception Reporting Form
 
http://www.virginia.edu/vprqs/irb/hsr_forms.html
 
Go to 3rd bullet from the bottom.

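### The adverse event record takes only events judged both related and serious, so serious events judged unrelated, and on a literal reading possibly related ones, stay off it

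*Combined protocol and SAP*

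**What the plan says.** All references are to the combined protocol and SAP; numbered sections are those of its Data and Safety Monitoring Plan.

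- **Section 3.1** says that not all adverse events will be recorded. The criterion is "Only adverse events that are deemed related AND serious".
- **Section 1.1** counts an undesirable event as an adverse event "only if the event is considered to be related" to the intervention.
- **Section 1.2** defines seriousness by outcome, for example an event that "requires or prolongs inpatient hospitalization". It sets no relatedness condition.
- **The relatedness scale under section 3.3** has three levels, assigned by the PI. Related means a clear link, Possibly related means there may be one, and Unrelated means there is clearly none.
- **Section 1.3** defines an unanticipated problem by three criteria that must all be met. The first is that it "Is unexpected in terms of nature, severity or frequency given the research procedures" and the population. The second is "Related or possibly related to participation in research". The third is greater risk than was known, or actual harm.
- **The section 3.7 reporting table** has one row for an "Internal, Serious, related, Unexpected adverse event" and another for "Unanticipated Problems that are not adverse events or protocol violations".
- **Biomedical Research, item 1** says that "nutritional intake and in hospital complications will be recorded", and that ICU and hospital stay will be noted.
- **Section 5.1** names no safety overseer other than the PI.

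**The concern.** In a randomised placebo-controlled trial, the most useful safety summary is a complete list of serious events by arm. It does not depend on anyone deciding, case by case, what caused each event. Here that decision comes first and determines whether the event enters the adverse event record at all. After major spine surgery many serious events will have a surgical explanation, so the decision matters often. The PI makes it and is also the only person reviewing safety in aggregate. An event left off the form cannot be recovered from the adverse event record after unblinding. The rule also turns on the word related, and the plan does not say whether that includes the middle level of its own scale.

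**Working it through.** No arithmetic decides this point. The check applies sections 1.1 and 3.1 and the relatedness scale to each combination of seriousness and relatedness.

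| Event | Relatedness | On the adverse event record? |
|---|---|---|
| Serious | Related | Yes |
| Serious | Possibly related | Not settled; no if related means a clear link |
| Serious | Unrelated | No |
| Not serious | Any of the three levels | No (3 combinations) |

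Of six combinations, 1 is clearly recorded, 4 are clearly not, and 1 is undetermined. For the undetermined one, the literal reading is exclusion. The scale separates the two levels, and section 1.3 names both where both are meant, whereas sections 1.1 and 3.1 and the serious-event row of section 3.7 say only related.

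Next, the other routes by which the two serious combinations might be captured:

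1. **In-hospital complications (Biomedical Research, item 1).** These are recorded with no relatedness or seriousness filter. Dosing ends at discharge or earlier, and sections 3.5 and 3.6 run adverse event recording from the start of the intervention to the end of study drug or participation, so the periods largely overlap. But the term is not defined. Statistical Considerations, items 2, 4 and 5, give a general method for categorical data but name no analysis or listing of complications.
2. **Unanticipated problems (sections 1.3 and 3.7).** A possibly related event can take this route only if it is also unexpected and meets the risk-or-harm criterion. A serious possibly related event that is expected in this population does not qualify. An event judged unrelated never does.

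What has no defined record is therefore any serious event judged unrelated and, on the literal reading, any serious possibly related event that is expected.

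One interaction affects the fix. The unanticipated-problem row of section 3.7 excludes adverse events. If section 1.1 is widened and nothing else changes, a possibly related event becomes an adverse event and could leave that row without clearly entering the serious-event row, which says only related.

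Finally, what a complete list could show. The allocation ratio is not stated; assume 30 per arm from the 60 to be recruited. The two-sided Fisher exact p-value for k events against 0 is 2 × C(30,k) / C(60,k):

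- k = 5: 2 × 142,506 / 5,461,512 = 0.052
- k = 6: 2 × 593,775 / 50,063,860 = 0.024

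Nothing short of 6 against 0 reaches p < 0.05 when one arm has no events, so the list is worth having as description and not as a test.

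**The case against.** The strongest reply is that most of these events are captured anyway. A death or a complication that prolongs the stay would ordinarily count as an in-hospital complication, and could be listed by arm once the blind is broken. That stands against any claim that the events are lost. It does not answer the point that complications have no definition and no planned listing, so their completeness rests on habit.

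A second reply is that restricted recording is an option the form itself offers, chosen for a marketed drug. That is fair. This is a design choice that could be better, not a breach.

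Stronger readings that a reader might infer, and why they fail:

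- **Bias between arms.** The trial is double-blind, and section 2.5 keeps the database blinded until the data are complete. Relatedness calls should not depend on the arm.
- **A heart attack would go unrecorded because surgery is another plausible cause.** The scale keeps Unrelated for events clearly not due to the intervention. An event with two plausible causes fits Possibly related and, if unexpected, can reach the IRB as an unanticipated problem.
- **The safety results could not be compared with the published data in item 13b of the Pharmacy-Approved Drug appendix.** The only rate given there is for dyspepsia, and events count to 7 days after the last dose. Recording all serious events within this trial's period would not make the two comparable.
- **The Unrelated level contradicts section 1.1.** The scale can be read as the tool for deciding whether an event meets section 1.1, so this is loose wording at most.

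**Conclusion.** The point holds as one of completeness. Sections 1.1 and 3.1 keep serious events judged unrelated off the adverse event record. Read with the scale, they also leave off serious possibly related events, unless related is meant more widely than the scale defines it. The other routes catch some of these events but give no defined, listed record of them.

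The size cannot be derived: the documents give neither a serious event rate nor the share judged unrelated. Any count would rest on assumed rates, and would be of events missing from the adverse event form, not of events shown to be missing from the trial data. The primary analysis is not affected. The change is worth making because it is cheap and yields a safety record that does not depend on attribution.

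**What to change.** 1. In section 3.1, record all serious events meeting the outcome criteria of section 1.2, regardless of judged relatedness, within the existing recording period.
2. Amend the relatedness condition in section 1.1 to match.
3. Keep the three-level scale as a recorded attribute of each event.
4. In the serious-event row of section 3.7, state whether possibly related counts as related.
5. State that events meeting section 1.3 are still reported as unanticipated problems, so that widening section 1.1 does not remove them from that row.
6. Define in-hospital complications, and plan a descriptive listing by arm of these and of the serious events at the end of the study, without testing.

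The cost is protocol wording and some added adverse event forms. As an illustration only, if 5% to 20% of the 60 subjects had a serious event (an assumed range), forms would be needed for 60 × 0.05 = 3 to 60 × 0.20 = 12 subjects, including those already recordable as related. No new visit, test or follow-up is required.

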3.2 How will adverse event data be collected/recorded? Check all that apply

Paper AE forms/source documents

3.3. How will AEs be classified/graded? Check all that apply

Mild/Moderate/Severe

Serious/Not serious Required for all protocols

- **What scale will the PI use when evaluating the relatedness of adverse events to the study participation?**

The PI will determine the relationship of adverse events to the study using the following scale:

Related: AE is clearly related to the intervention
 Possibly related: AE may be related to the intervention
 Unrelated: AE is clearly not related to intervention

3.5 When will recording/reporting of adverse events/unanticipated problems begin?

After subject begins study drug/ device placement/intervention /study-related procedure/specimen collection

3.6 When will the recording/reporting of adverse events/unanticipated problems end?

End of study drug/device/intervention/participation

3.7 How will Adverse Events, Unanticipated Problems, Protocol Violations and Data Breaches be reported? Complete the table below to answer this question

Type of Event	To whom will it be reported:	Time Frame for Reporting	How reported?

Any internal event resulting in death that is deemed DEFINITELY related to (caused by) study participation An internal event is one that occurs in a subject enrolled in a UVa protocol
	IRB-HSR	Within 24 hours	IRB Online and phone call www.irb.virginia.edu/

Internal, Serious, related, Unexpected adverse event
	
IRB-HSR
	
Within 7 calendar days from the time the study team received knowledge of the event.
 
Timeline includes submission of signed hardcopy of AE form.
	
IRB Online
 
www.irb.virginia.edu/

Unanticipated Problems that are not adverse events or protocol violations This would include a Data Breach.
	
IRB-HSR
	
Within 7 calendar days from the time the study team received knowledge of the event.
	
Unanticipated Problem report form.
 
http://www.virginia.edu/vprqs/irb/HSR_docs/Forms/Reporting_Requirements-Unanticipated_Problems.doc)

Protocol Violations/Noncompliance The IRB-HSR only requires that MAJOR violation be reported, unless otherwise required by your sponsor, if applicable.
 
OR
 
Enrollment Exceptions See definition- only allowed if there is a commercial sponsor or a DSMB that has granted the enrollment exception.
	
IRB-HSR
	
Within 7 calendar days from the time the study team received knowledge of the event.
	
Protocol Violation, Noncompliance and Enrollment Exception Reporting Form
 
http://www.virginia.edu/vprqs/irb/hsr_forms.html
 
Go to 3rd bullet from the bottom.


Data Breach
	
The UVa Corporate Compliance and Privacy Office
 
ITC: if breach involves electronic data
 
Police if breach includes items that are stolen:
 
Stolen on UVA Grounds
	
As soon as possible and no later than 24 hours from the time the incident is identified.
 
As soon as possible and no later than 24 hours from the time the incident is identified.
 
IMMEDIATELY.
	
UVa Corporate Compliance and Privacy Office- [contact]
 
ITC: Information Security Incident Reporting procedure, http://www.itc.virginia.edu/security/reporting.html
 
UVa Police-Phone- [contact]

	OR Stolen off UVa Grounds- contact police department of jurisdiction of last known location of PHI		
--	---	--	--

4. How will the endpoint data be collected/recorded. Check all that apply

- Protocol specific case report forms
- Source documents
- Database: to be stored on the "O" drive

5. Data and Safety Oversight Responsibility

5.1. Who is responsible for overseeing safety data for this study?

INSTRUCTIONS:

e.g. Who is looking at data in aggregate form to identify trends?

Check all that apply

- No additional oversight body other than PI at UVa Skip question 5.2

5.2. What is the composition of the reviewing body and how is it affiliated with the sponsor? *n/a*

5.3. What items will be included in the aggregate review conducted by the PI?

- All adverse events
- Unanticipated Problems
- Protocol violations/Issues of noncompliance
- Audit results
- Application of dose finding escalation/de-escalation rules

These should be outlined under 2.4.

- Application of study designed stopping/decision rules
- Early withdrawals
- Whether the study accrual pattern warrants continuation/action
- Endpoint data

a. How often will aggregate review occur?

For additional information on aggregate review see:

www.virginia.edu/vpr/irb/hsr/continuations.html#aggreview

- Annually

5.5. How often will a report, regarding the outcome of the review by the DSMB/DSMC, be sent to the UVa PI? n/a

5.6. How will a report of the information discussed in question 5.4 OR 5.5 be submitted to the IRB?

 x Part of IRB-HSR continuation status form

Risk/ Benefit Analysis

1. What are the potential benefits for the participant as well as benefits which may accrue to society in general, as a result of this study?

Opiates are often necessary in high doses, and may be associated with significant side effects. Such side effects may include urinary retention, altered mental status, depressed respiratory drive, and constipation, and may lead to reduced nutritional intake in the postoperative period. The potential benefit for the participant may be the reduction of these side effects.

We have chosen to study the reconstructive spinal surgery patient population because we believe that the use of alvimopan in these patients at the University of Virginia will give the scientific community significant insight into the broader applicability of this drug into other surgical populations, the impact of this drug on the perception of pain (as opposed to simply the consumption of opioids), and its impact on total hospital charges, resource utilization, and functional outcomes

2. Do the anticipated benefits justify asking subjects to undertake the risks?

The risks are those of opioids and the risks of the study drug. The benefit may improve bowel outcomes thus the risk benefit ratio is favorable.

Bibliography

